- b For all fitusiran dosing administered at the study center or at home, LFT results are to be obtained within 7 days prior to dosing and results are to be reviewed prior to each dose. The frequency of predose LFT monitoring may be decreased to quarterly for patients who have negative hepatitis C antibody titers and meet specific criteria defined in Section 6.5.1.1.
- c A directed physical examination will be performed predose on dosing days checked in the table. See Section 9.1.5 for assessments to be performed during a directed physical examination.
- d Vital signs include blood pressure, heart rate, body temperature (oral, tympanic, or axillary), and respiratory rate. Vital signs will be measured in the seated or supine position after the patient has rested comfortably for 10 minutes. Vital signs will be collected predose on dosing days checked in the table.
- e 12-lead ECGs will be performed in the supine position after the patient has rested comfortably for 10 minutes. ECG will be performed before blood sample collection.
- f Full Hepatic Tests (Table 10) must be performed in all patients once annually. FibroScan (or FibroTest with APRI) testing must be performed in all patients found to have positive hepatitis C antibody titers.
- g Blood samples will be collected predose on dosing days checked in the table. Biochemistry, hematology, and coagulation are described in Section 9.1.7.1.
- h Sample for urinalysis will be collected predose on dosing days checked in the table. Urinalysis parameters are described in Section 9.1.7.3.
- i Blood samples will be collected predose on dosing days checked in the table.
- i As determined by Nijmegen modified Bethesda assay.

- k When patients reinitiate the study at their 80 mg or 50 mg monthly dose (no dose change) they will have their AT, TG, and coagulation measured monthly for 6 months. Upon the first AT activity level <15%, the patient must have another AT activity level sample drawn within 1 week of site receipt of the results.
- Will include review of entries, (symptoms of bleed events, bleed causality, bleed severity, factor or BPA doses administered), whether site contact occurred regarding treatment of bleeds, and review of patient bleed management plan and recommendations and requirements for site contact regarding dosing.
- m Perioperative assessment of safety and hemostatic efficacy only in patients undergoing major operative procedures while on study (see Table 4).
- n AEs including signs and symptoms of thrombosis will be evaluated continuously (see Section 5.5).
- o All study patients that are consenting to this procedure are requested to undergo testing for SARS-CoV-2 (virus responsible for COVID-19), which should include both RT-PCR and antibody testing. Note: Rapid test may be used if RT-PCR is not available. These tests should be performed as early as possible during the study, except for patients who have undergone COVID-19 vaccination, after which antibody testing is no longer required. Alternatively, historical test results may be provided under certain circumstances as defined by Sponsor.
- p Only for patients who would complete the study as per current schedule before having at least 18-calendar months treatment under the new dose and regimen. For patients continuing beyond Month 72 for this reason, when 18-calendar months post resuming treatment is reached, the EOT visit should be completed, followed by the EOS and AT follow-up period.

Table 3: Modified IMP Regimen Schedule of Assessments (Year 1, 2, 3)

]	rea	atm																			-		
					}	/ea	r 1											1	Ye	ar 2	2										Y	ear	3						
Time from modified IMP regimen re-start ^a	Day of dose re-start	PRM1	PRM2	PRM3	PRM4	PRM5	PRM6	PRM7	PRM8	PRM 9	PRM10	PRM11	PRM12	PRM13	PRM14	PRM15	PRM16	PRM17	PRM18	PRM19	PRM20	PRM21	PRM22	PRM23	PRM24	PRM25	PRM26	PRM27	PRM28	PRM29	PRM30	PRM31	PRM32	PRM33	PRM34	PRM35	PRM36	EOS/ET	AT FU
PR Study Day (±Visit Window)	1	29 ±7	57 ±7	85 ±7	113 ±7	141 ±7	169 ±7	197 ±7	225 ±7	253 ±7	281 ±7	309 ±7	337 ±7	365 ±7	393 ±7	421 ±7	449 ±7	477 ±7	205 ±7	533 ±7	561 ±7	589 ±7	617 ±7	645 ±7	673 ±7	701 ±7	729 ± 7	757 ±7	785 ±7	813 ±7	841 ±7	869 ±7	2∓ Z	925 ±7	9 53 ±7	981 ±7	1009 ±7		
Re-sign Informed Consent	X																																						
FVIII or FIX Levels	X																																						
Study Drug Administration Q2M ^b	X		X		X		X		X		X		X		X		X		X		X		X		X		X		X		X		X		X		X		
Study Drug Administration QM ^b	X	X	X	X	X	X	X	X	X	X	X	X	X	X	X	X	X	X	X	X	X	X	X	X	X	X	X	X	X	X	X	X	X	X	X	X	X		
Directed Physical Exam ^c	X		X		X		X		X		X		X		X		X		X		X		X		X		X		X		X		X		X		X	X	
Body Weight	X		X		X		X		X		X		X		X		X		X		X		X		X		X		X		X		X		X		X	X	
Vital Signs ^d	X		X		X		X		X		X		X		X		X		X		X		X		X		X		X		X		X		X		X	X	
12-Lead ECG ^e	X						X						X												X												X	X	

	Treatment Period Year 1 Year 2 Year 3																																						
					1	Yea	r 1																								Y	ear	3						
Time from modified IMP regimen re-start ^a	Day of dose re-start	PRM1	PRM2	PRM3	PRM4	PRM5	PRM6	PRM7	PRM8	PRM 9	PRM10	PRM11	PRM12	PRM13	PRM14	PRM15	PRM16	PRM17	PRM18	PRM19	PRM20	PRM21	PRM22	PRM23	PRM24	PRM25	PRM26	PRM27	PRM28	PRM29	PRM30	PRM31	PRM32	PRM33	PRM34	PRM35	PRM36	EOS/ET	AT FU
PR Study Day (±Visit Window)	1	7 ∓ 62	21 ± 7	85 ±7	113 ±7	141 ±7	169 ±7	2 + 2 6 1	225 ±7	7 ∓ 2 53 ∓ 7	281 ±7	309 ±7	337 ±7	365 ±7	393 ±7	421 ±7	449 ±7	477 ±7	205 ±7	533 ±7	561 ±7	589 ±7	617 ±7	645 ±7	673 ±7	701 ± 7	729 ±7	∠∓ LS L	∠ ∓ S 8 L	813 ±7	841 ±7	2∓ 698	2 ± 2 ± 2 ± 2 ± 2 ± 2 ± 2 ± 2 ± 2 ± 2 ±	925 ±7	7 ± €2 6	981 ±7	1009 ±7		
Liver Status Studies ^f													X, 1	mus	t be	pei	for	med	on	ce a	t ar	ny c	linic	vis	it ^f														
Inhibitor Status ⁹	X												X												X												X		
Biochemistry and hematology Assessments ^h	X		X		X		X		X		X		X				X				X				X						X						X	X	
Liver function testsh	X	X	X	X	X	X	X	X	X	X	X	X	X	X	X	X	X	X	X	X	X	X	X	X	X	X	X	Xi	X	Xi	X	X	X	Xi	X	X	X	X	
Urinalysis ^j	X						X						X												X												X	X	
Antidrug Antibodies ^k	X						X						X												X												X		
Coagulation ^h	X	X	X	X	X	X	X	X	X	X	X	X	X				X				X				X				X				X				X	X	
Plasma AT Activity ^k	X	X	X	X	X	X	X	X	X	X	X	X	X				X				X				X				X				X				X	X	X
Plasma TG ^k	X	X	X	X	X	X	X	X	X	X	X	X	X				X				X				X				X				X				X	X	
EQ-5D-5L Questionnaire and Haem-A-QoL	X						X						X						X						X						X						X		
Patient Education Module Training																То	be c	com	plet	ted o	onc	e m																	
Patient Diary						Re	viev	v w	ith 1	pati	ent	at e	ach	do	sing	g, an	d co	onta	ct e	ever	y 2	wee	eks ((±4 o	days	s) in	bet	wee	en fi	itusi	ran	dos	sing						
Bleed Management Review ⁿ						Re	viev	v w	ith 1	pati	ent	at e	ach	do	sing	g, an	d co	onta	ct e	ever	y 2	wee	eks ((±4 o	days	s) in	bet	wee	en f	itusi	ran	dos	sing						
Perioperative Assessment ⁰																		C	Cont	tinu	ous																		

																7	Γrea	atm	ent	Per	iod																		
					}	Year	r 1												Ye	ar 2	2										Y	ear	3						
Time from modified IMP regimen re-start ^a	Day of dose re-start	PRM1	PRM2	PRM3	PRM4	PRM5	PRM6	PRM7	PRM8	PRM 9	PRM10	PRM11	PRM12	PRM13	PRM14	PRM15	PRM16	PRM17	PRM18	PRM19	PRM20	PRM21	PRM22	PRM23	PRM24	PRM25	PRM26	PRM27	PRM28	PRM29	PRM30	PRM31	PRM32	PRM33	PRM34	PRM35	PRM36	EOS/ET	AT FU
PR Study Day (±Visit Window)	1	29 ±7	57 ±7	85 ±7	113 ±7	141 ±7	169 ±7	197 ±7	225 ±7	253 ±7	281 ±7	309 ± 7	337 ±7	365 ±7	393 ±7	421 ±7	449 ±7	477 ±7	505 ±7	533 ±7	561 ±7	589 ±7	617 ±7	645 ±7	673 ±7	701 ± 7	729 ±7	7 5 7 ±7	785 ± 7	813 ±7	841 ±7	869 ±7	2 ± 2 ± 2 ± 2 ± 2 ± 2 ± 2 ± 2 ± 2 ± 2 ±	925 ±7	953 ±7	981 ±7	1009 ±7		
Adverse Events ^p																		C	ont	inu	ous																		
Concomitant		Continuous																																					
Medications ^q																																							
COVID-19 Testing																Α	nyt	ime	du	ring	the	stu	dy ^r																

Abbreviations: AE=adverse event; APRI=Aspartate aminotransferase to Platelet Ratio Index; AT=antithrombin; BPA=bypassing agent; CRF=Case Report Form; CD4=cluster of differentiation 4; ECG=electrocardiogram; EOS=End of Study; EOT=End of Treatment; EQ-5D-5L=EuroQoL 5-Dimensions, 5-Levels Questionnaire.; ET=Early Termination; exam=examination; FVIII=factor VIII; FIX=factor IX; Haem-A-QoL=Haemophilia Quality of Life Questionnaire; HIV=human immunodeficiency virus; LFT=Liver function test; INR=international normalized ratio; M=Month; PK=pharmacokinetics; PR=post-restart; PT=prothrombin time; SC=subcutaneous; TG=thrombin generation; treat=treatment.

- Notes:
 - When scheduled at the same time points, assessments of vital signs and 12-lead ECGs should be performed first, before the physical examinations and blood/urine sample collections.
 - Where study assessments overlap with the parent study, the assessments only need to be performed once.
- a This schedule applies for patients meeting criteria for adjusted dosing regimen. Upon each dose adjustment, the patient will restart the schedule (For dose adjustment from 50 mg Q2M to 50 mg QM, the patient will restart at PR M1 as their Month 6 visit under 50 mg will serves as their PR Study Day 1. For dose adjustment from 50 mg QM to 80 mg QM, the patient will restart at PR Study Day 1). The duration that the patient must continue in the study post modified IMP dose/frequency re-start depends on the re-start time-point relative to the overall study start for each individual patient to ensure an overall duration of fitusiran administration of approximately 72 months or 18 calendar months after restarting dosing post dosing pause (whichever is longer). Thus, when the patient reaches the latter of 72 months of study participation or 18 calendar months post dosing restart, the EOT visit should be performed, followed by the EOS and AT follow-up period.
- b Patients will follow either the Q2M or QM dosing regimen according to the dose adjustment rules; see Section 6.5.1.3. SC administration of study drug as per Pharmacy Manual. From Year 3 onwards, the frequency of predose LFT monitoring may be decreased for patients who have negative hepatitis C antibody titers and meet specific criteria defined in Section 6.5.1.1.
- c On Day 1, a directed physical examination will be performed at predose and 6 hours postdose. On all other dosing days checked in the table, the directed physical examination will be performed predose. See Section 9.1.5 for assessments to be performed during a directed physical examination.
- d Vital signs include blood pressure, heart rate, body temperature (oral, tympanic, or axillary), and respiratory rate. Vital signs will be measured in the seated or supine position after the patient has rested comfortably for 10 minutes. On Day 1, vital signs will be collected predose and at 6 hours (±30 minutes) postdose. On all other dosing days checked in the table, vital signs will be collected predose.
- e 12-lead ECGs will be performed in the supine position after the patient has rested comfortably for 10 minutes. 12-lead ECGs will be performed before blood sample collection.
- f Full Hepatic Tests (Table 9) Sample must be performed in all patients once, at Screening (if newly enrolled) or at next scheduled clinic visit (if patient has already completed a clinic visit) and annually thereafter. FibroScan (or FibroTest with APRI) testing must be performed in all patients found to have positive hepatitis C antibody titers
- g As determined by Nijmegen modified Bethesda assay.
- h Blood samples will be collected predose at visits checked in the table. Biochemistry, hematology, and coagulation are described in Section 9.1.7.1.

- i LFT testing is not required at these visits for patients on the every other month dosing regimen or for patients who meet the criteria for every other month pre-dose LFT monitoring with dosing described in Section 6.5.1.1
- j Sample for urinalysis will be collected predose at visits checked in the table. Urinalysis parameters are described in Section 9.1.7.3.
- k Blood samples will be collected predose at visits checked in the table. ADA samples will be collected within 240 minutes before dosing according to the schedule in Table 15 and Table 16. At each dose level, upon the first AT activity level <15%, the patient must have another AT activity level sample drawn within 1 week of site receipt of the result.
- / Assessments will be performed predose at visits checked in the table, where available.
- m To be completed once, prior to dosing with fitusiran.
- n Will include review of entries, (symptoms of bleed events, bleed causality, bleed severity, factor or BPA doses administered), whether site contact occurred regarding treatment of bleeds, and review of patient bleed management plan and recommendations and requirements for site contact regarding dosing.
- o Perioperative assessment of safety and hemostatic efficacy only in patients undergoing major operative procedures while on study (see Table 4).
- p AEs including signs and symptoms of thrombosis will be evaluated continuously (see Section 5.5).
- q Medication(s) will be recorded as concomitant if any of the following apply: 1) medication is ongoing from a previous fitusiran clinical trial; 2) medication started between a previous fitusiran clinical trial and the present study; or 3) medication started after signing informed consent for the present clinical trial.
- r All study patients that are consenting to this procedure are requested to undergo testing for SARS-CoV-2 (virus responsible for COVID-19), which should include both RT-PCR and antibody testing. Note: Rapid test may be used if RT-PCR is not available. These tests should be performed as early as possible during the study, except for patients who have undergone COVID-19 vaccination, after which antibody testing is no longer required. Alternatively, historical test results may be provided under certain circumstance as defined by Sponsor.

Table 4: Perioperative Schedule of Assessments in Patients Undergoing Major Operative Procedures

		Perioperati	ive Evaluation I	Period ^a	
	Preoperative Screening	Dental/Surgical Procedure Visit	Postoperative Visit 1	Postoperative Visit 2	Postoperative Visit 3
	SDay -3 to -1	SDay 0	SDay 1 ^b	SDay 2 to 14 ^c	SDay 28 (up to 28 days) ^k
Hemostatic/ Thromboprophylaxis Treatment Plan	X				
Directed Physical Examination ^d	X				X
Vital Sign Measurements ^e	X				X
Clinical Laboratory Assessments ^f	X	X ^h	X	X	X
TG	X	χ g, h	X ^g	Xg	Xg
AT Activity Level	X	X ^{i, h}			
FVIII/IX Levels ^g	X	Xg, h	X ^g	Xg	Xg
Hemostatic efficacy (Perioperative Questionnaire)		χj, h	X	X	
Completion of Hemostatic Treatment Coverage	Li (GD 2) GI			X ^k	Xk

Note: Any operative procedure dates (SDay -3 to SDay 28) may overlap with the study Schedule of Assessments (Table 1) Abbreviations: APTT=activated partial thromboplastin time; AT=antithrombin; BPA=bypassing agent; PF=prothrombin fragment; SDay=surgery day; TG=thrombin generation

- a During Perioperative Evaluation Period, adverse events and concomitant medications will be collected continuously per study Schedule of Assessments (Table 1).
- b Assessments to be completed within 24 hours (±12 hours) from the time of end of the procedure.
- c Visit may occur anytime between SDay 2 to SDay 14, postoperatively, on a day to be determined by the Investigator. If multiple visits are planned between Days 2-14 after the procedure, the Hemostatic efficacy (by using perioperative questionnaire) for Postoperative Visit 2 should be completed on the day of the last visit.
- d Directed physical examination (see Section 9.1.5).
- e Vital signs will be the same as conducted in the clinical study protocol Schedule of Assessments (Table 1).
- f Clinical laboratory assessments will include coagulation, hematology, and biochemistry (Table 10).
- g If factor or BPA administration and the surgical procedure occur at the study center visit, one sample should be collected pre-factor/BPA administration and two samples should be collected post-factor/BPA administration on the day the procedure. The pre-factor/BPA sample may be collected any time before factor or BPA administration. The post-factor/BPA samples should optimally be collected at 10 min (±5 min) and 60 min (±10 min) after factor or BPA administration. The actual times of collections should be recorded.
- *h* If the operative procedure is not performed at a study center, the assessment is recommended.
- i Not necessary if captured at preoperative screening.
- j Hemostatic efficacy is to be assessed intraoperatively with the perioperative questionnaire on the day of the procedure (SDay 0); assessment may be completed up to 8 hours postoperatively. The Hemostatic efficacy (by using perioperative questionnaire) will also be completed at Postoperative Visit 1 and Visit 2. It is recommended that the Investigator complete this assessment in consultation with the surgeon or dentist who performed the operative procedure.
- k The date/time of when perioperative hemostatic treatment and thromboprophylaxis (if applicable) coverage was completed will be captured. If hemostatic treatment and thromboprophylaxis are completed at Postoperative Visit 2, the date/time of completion should be recorded, and the SDay 28 visit is not required.

Table 5: Bleeding Episode Assessments - Unscheduled Visit

	Predose	Postdose 10 min (±5 min)	Postdose 60 min (±5 min)
Directed Physical Examination ^a	X		
Vital Signs	X		
AT	X		
FVIII/IX Levels	X	X	X
TG	X	X	X
Coagulation	X	X	X
Hematology	X	X	X
Optional Imaging ^b	X		

Abbreviations: AT=antithrombin; FVIII=factor VIII; FIX=factor IX; TG=thrombin generation

a See Section 9.1.5 for assessments to be performed during a directed physical examination.

b Investigator to consider confirmation of bleed via ultrasound or other imaging modality at clinical study centers where appropriate equipment and staff with related expertise is available.

TABLE OF CONTENTS

< <prc< th="">DTOCOL AMENDMENT SUMMARY OF CHANGES	3	</prc<>	DTOCOL AMENDMENT SUMMARY OF CHANGES	3
DOCU	MENT HISTORY	3
OVER	ALL RATIONALE FOR THE AMENDMENT	3
PROTO	OCOL SYNOPSIS	9
TABLE	E OF CONTENTS	25
LIST O	OF TABLES	30
LIST O	OF FIGURES	31
LIST O	OF ABBREVIATIONS AND DEFINITIONS OF TERMS	32
1	INTRODUCTION	35
1.1	DISEASE OVERVIEW	35

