If the need for emergency or urgent major surgery arises during the trial, the patient should be managed medically according to the guidelines above. If an fitusiran dose is scheduled to occur on or in close proximity to the day of surgery, or anytime during the perioperative period, the dose should be withheld. The Perioperative Evaluation Period is defined as the day of the surgery through the final day on which supplemental hemostatic or antithrombotic treatments are administered as part of the perioperative treatment plan. Fitusiran dosing may be resumed at the next scheduled visit following the Perioperative Evaluation Period at the discretion of the Investigator. If multiple consecutive doses of fitusiran are withheld, the Investigator will consult with the study Medical Monitor, who will determine if the patient may continue on study.

Perioperative assessments will be performed in patients undergoing major surgery during the study as described in Section 8.4, and as scheduled in Table 4.

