6.5.1.3 Antithrombin level criteria for a dose adjustment

With the introduction of the new dose and regimen with Protocol Amendment 07 following the global program dosing pause implemented by Sponsor in 2020, patients will receive fitusiran treatment according to the below antithrombin level scenarios and criteria. See the rationale for a new dosing justification in Section 1.5. Dose modification rules are detailed in the section below and displayed in Figure 1 and Figure 2.

A) Dose restart

- a) Restart at 50 mg Q2M
- Patients that reach AT activity levels ≥22% (per central laboratory),
- Patients previously exposed to fitusiran at a dose of 50 mg QM or 80 mg QM with more than one AT activity level <15% (per central laboratory) at any time during fitusiran treatment,
- Patients will resume dosing at a dose of 50 mg Q2M and follow the modified IMP regimen SoAs (Table 3).
- b) Restart at 50 mg QM or 80 mg QM (prior dose)
- Patients that reach AT activity levels ≥22% (per central laboratory),
- Patients previously exposed to fitusiran at a dose of 50 mg QM or 80 mg QM with no more than one AT activity level <15% (per central laboratory) at any time during fitusiran treatment (based on at least 3 months of prior AT measurements),
- Participant may have the option to remain on that dose and follow the SoAs in Table 1 and Table 2.

B) Dose escalation

- a) Dose escalation to 50 mg QM
- After a period of dosing at 50 mg Q2M,
- Based on 2 steady state AT values >35% at the 50 mg Q2M dosing regimen,

- At least 2 of the 3 AT samples taken pre-dose at PR Month 4, PR Month 5 and PR Month 6 must be >35% to meet the escalation rule,
- Patients who previously had more than 1 AT value <15% at the 50 mg QM dose are not eligible to re-escalate to this dose level,
- If escalation rules are met, patient will receive the 50 mg dose at PR Month 7 (this will be considered the PR Month 1 of 50 mg QM, ie, the second 50 mg QM dose).

Note: If any of the doses prior to PR Month 6 are missed, then the decision-making for escalation must be shifted accordingly.

- b) Dose escalation to 80 mg QM
- After a prior escalation to the 50 mg QM dosing regimen,
- Based on 2 steady state AT values >35% at the 50 mg QM dosing regimen,

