- c. Missing two consecutive doses in LTE14762 (eg, a participant skips at least two consecutive scheduled doses): If participant under Q2M regimen before the dose interruption, then exclude events occurring on dates starting from the date of the last dose before the dose interruption + 57 days to the date of the dose resumption + 56 days. If participant under QM regimen before the dose interruption, then excluded events from the date of the last dose before the dose interruption + 29 days to the date of the dose resumption + 28 days. The missing two consecutive doses will be considered separately before and after the dose pause in 2020.
- d. Fitusiran treatment discontinuation in LTE14762: Exclude events occurring on any dates starting from the date of the last dose +29 days if the last dose regimen is QM (ie, until the end of the study.) If the last dose regimen is Q2M, then the start date of this intercurrent event should be last dose + 57 days.

II. Perioperative period of major surgery and major trauma is defined as the day of the surgery or trauma through the final day on which supplemental hemostatic or antithrombotic treatments are administered as part of the perioperative treatment plan.

III. Perioperative period of minor surgery is defined as the perioperative period of surgery as defined for major surgery (see above) or to 72 hours from the end of surgery, whichever is later.

IV. Period of antithrombin treatment defined as the first day of antithrombin treatment through the final day on which antithrombin or other anticoagulant therapies are administered +5 half-lives.

V. After treatment with emicizumab.

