6.8.4 Vital signs and physical examination

Descriptive statistics will be provided for vital signs, including blood pressure, pulse rate, oral body temperature and respiration rate. For data under the original dose and regimen, the descriptive summary will be provided from the LTE14762 study baseline up to the 2017 clinical dose pause. For data under the revised dose, the summary will be provided from the dose resumption up to the end of study. A summary table of PCSA will be provided. Abnormal PE results will be listed. All the vital sign and physical examination summary tables will not include assessment taken during the major surgery period. These results will be presented in listings with identifier of major surgery.

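### Table 4 footnote k waives the SDay 28 visit without moving its physical examination and vital signs, so a waived patient has neither scheduled in Table 4 after major surgery

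*Protocol*

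**What the plan says.** Protocol Table 4 has five perioperative columns: preoperative screening, SDay 0, SDay 1 (Postoperative Visit 1), SDay 2 to 14 (Visit 2) and SDay 28, up to +28 days (Visit 3). The rows "Directed Physical Examination" and "Vital Sign Measurements" are ticked at screening and at Visit 3 only.

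Footnote k drops Visit 3 for patients whose hemostatic and thromboprophylactic cover has ended: "completed at Postoperative Visit 2, the date/time of completion should be recorded, and the SDay 28 visit is not required". The only item it transfers to Visit 2 is the date and time of completion.

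The synopsis and Protocol 3.1 and 8.4 describe the SDay 28 visit as one that takes place, with the purpose of documenting when coverage ended. They mention neither the waiver nor the two clinical rows.

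Protocol 5.7 runs the Perioperative Evaluation Period from the day of surgery to "the final day on which supplemental hemostatic or antithrombotic treatments are administered as part of the perioperative treatment plan". SAP 6.3 uses the same end point: "Perioperative period of major surgery and major trauma is defined as the day of the surgery or trauma through the final day" of such treatment. SAP 6.8.4 adds: "All the vital sign and physical examination summary tables will not include assessment taken during the major surgery period". Those results go to listings with a surgery flag.

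**The concern.** The footnote settles the administrative purpose of the SDay 28 visit and says nothing about the two clinical assessments that Table 4 places there. Protocol 9.1.5 makes the directed examination the hands-on check for thrombosis and bleeding. It sends surgical patients back to Table 4 for timing, so there is no second source for a postoperative time point.

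The patients affected have lowered antithrombin (AT) and a recent major operation. Suspected or confirmed thrombosis is an adverse event of special interest (9.2.7). Under 5.7, fitusiran may resume at the next scheduled visit after the perioperative period. What is at stake is one scheduled bedside check per waived operation. No efficacy endpoint or dosing rule depends on it.

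**Working it through.** The plan gives no figure to reproduce. The check is a count of Table 4 cells followed by the spacing of routine visits.

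**Step 1. Scheduled assessments after SDay 0 in Table 4.** The laboratory row has an entry in all five columns, which confirms the column alignment.

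| Row | Visit 3 held | Visit 3 waived |
|---|---|---|
| Directed physical examination | 1 (Visit 3) | 0 |
| Vital signs | 1 (Visit 3) | 0 |
| Clinical laboratory, TG, FVIII/IX levels (each) | 3 (Visits 1, 2, 3) | 2 (Visits 1, 2) |
| Hemostatic efficacy rating | 2 (Visits 1, 2) | 2 (Visits 1, 2) |

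Only the first two rows fall to zero.

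**Step 2. Does other text restore them?** Footnote c assigns only the hemostatic rating to the last Visit 2. Footnotes d and e define content, not timing. Sections 5.7, 8.4, 9.1.5 and 18.2.2 refer to Table 4. Section 9.1.3 makes extra vital signs discretionary, and 3.1 does the same for unscheduled visits.

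**Step 3. Latest next routine examination.** Days are nominal, visit windows are ignored, and surgery is taken to be the day after a routine visit (the worst case).

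- End of the Visit 3 window: 28 + 28 = SDay 56.
- Table 3, examinations on Days 1, 57, 113, ...: spacing 57 − 1 = 56 days, so latest 56 − 1 = SDay 55.
- Tables 1 and 2 from Month 24, examinations on Days 721, 901, 1081, ...: spacing 901 − 721 = 180 days, so latest 180 − 1 = SDay 179.

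SDay 55 lies inside the Visit 3 window. SDay 179 lies well outside it.

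**Step 4. What an examination at Visit 2 (SDay 2 to 14) would change.** It brings the first check forward by at most:

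- Table 3: 55 − 14 = 41 to 55 − 2 = 53 days.
- Tables 1 and 2 from Year 3: 179 − 14 = 165 to 179 − 2 = 177 days.

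The next routine visit does not move, so the same intervals can still pass between Visit 2 and that visit.

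**Step 5. Where the added data would be reported.** The surgery period ends on the last treatment day, not at the visit where completion is recorded. If treatment ends on the day of Visit 2, that visit is inside the period and its data go to listings only. If, for illustration, treatment ends on SDay 5 and Visit 2 is on SDay 12, the visit is after the period and SAP 6.8.4 does not exclude it. An SDay 28 assessment in a waived patient would have fallen after the period in either case.

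**The case against.** The strongest reply is that the waiver is deliberate. It was worded for clarity and operational convenience, the visit's stated purpose is to document the end of coverage, and that purpose is met once the date is recorded at Visit 2. This explains dropping the visit. It does not show that the examination was judged unnecessary, and no text says so.

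The second reply is that monitoring continues, and this stands. Adverse events are evaluated continuously. Patients are contacted every two weeks between doses and reviewed at each dosing (Tables 1 to 3, Protocol 5.3). Table 5 brings an examination and vital signs when a suspected bleed is evaluated and treated at the center, and 5.5 asks for a low threshold to evaluate possible thrombosis. A reader might infer from the 41 to 53 and 165 to 177 days that patients go unobserved for that long. The documents do not support that: these are intervals without a scheduled examination, not without follow-up.

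A reader might also infer that the patients with the deepest AT lowering wait longest. They do not. The 180-day spacing applies to patients kept on monthly dosing "with no more than one AT activity level <15% (per central laboratory) at any time during fitusiran treatment" (Protocol 6.5.1.3). Those with more than one such value restart at, or are reduced to, 50 mg every 2 months, and those restarting at that dose are sent to Table 3.

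Third, a Visit 2 examination would reach only patients whose coverage has ended, while those still on treatment wait for SDay 28. This is fair. It makes the change a cheap improvement rather than a full redesign of postoperative monitoring.

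**Conclusion.** The gap is real and small. A waived patient has 0 examinations and 0 sets of vital signs scheduled in Table 4 after major surgery instead of 1 each. Little is lost on Table 3. On Tables 1 and 2 from Year 3 the wait can reach nominal SDay 179, on the assumption that surgery falls the day after a routine visit; other timings give a shorter wait.

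The number affected cannot be estimated, because the documents give neither the number of operations nor the share waived. It is likely to be low: up to 48 patients may enroll, and 5.7 recommends postponing non-urgent major surgery until after the trial. Major surgery under 18.2.1 can also be as limited as a single molar extraction.

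A reader might conclude that anything collected at Visit 2 is bound to be lost from the summary tables. That holds only if treatment ends on the day of that visit. The point is of minor priority and rests on the Table 4 count, which is clear.

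**What to change.** Add to footnote k: *If the SDay 28 visit is waived, the directed physical examination and vital signs are performed at Postoperative Visit 2 (the last such visit if there are several).*

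This gives one scheduled postoperative check at SDay 2 to 14. It costs one sentence and a few minutes at a visit already taking place, with no new visit. It does not recreate an SDay 28 data point or shorten the interval to the next routine examination, and the SAP needs no change.

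Editorial only: add *unless waived per Table 4 footnote k* to the sentence on the SDay 28 visit in the synopsis and in Protocol 3.1 and 8.4.
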